12.1 History, physical examination and summary of laboratory investigations

A full **history** and **physical examination** will be done pre-IMP infusion, and thereafter as indicated in the study calendar. Examination also comprises statement on the performance score (Karnofsky index) of the patient and an ECG. *Lab tests* comprise a full blood count, urea, creatinine, electrolytes, glucose, protein, lipids, bilirubin, ALT (SGOT), AST (SGPT), AP, LDH, PCHE, ferritin, haptoglobin, CPK, troponin, lactate, standard urinalysis and coagulation assays. Coagulation assays comprise Quick, PTT, TZ, fibrinogen, fibrin-split-products, alpha 2 AP, AT III, D-dimers. Human anti-human antibodies (HAHA) will be tested for as indicated.

12.2 Clinical/blood assessment of toxicity

Clinical and blood assessment of toxicity will be done in intervals given in the study calendars during study period according to NCI CTCAE as stated above in section 9 of this protocol.

12.3 Pharmacokinetics

For pharmacokinetic studies the IMUBIND® assay will be used according to the protocol given by the manufacturer. Blood samples will be collected at the time points indicated in the calendars and stored frozen until testing. Since there is data from the first testings in patients treated that the half-life of tTF-NGR ($t_{1/2}$) is in the range of few hours, the time point given as "1h" in the calendars will be indeed multiple samplings in 30 min intervals for the first 5 hours.

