3.3 Trial Objectives

Primary Objectives

To evaluate the maximum tolerated dose (MTD) and the dose-limiting toxicity (DLT) of intravenously (iv) infused daily applications of tTF-NGR for 5 days every 3 weeks in patients with cancer (solid tumors and lymphomas), who had obtained all standard treatment known for their disease entity prior to entry on study.

Secondary Objectives

- 1. To determine the perfusion and vascular volume fraction of measurable tumor lesions versus normal reference tissue before and after tTF-NGR application by MRI as a biological surrogate parameter for biological activity of the IMP. Imaging will be preferentially done in the patients within the verification cohorts in at least one of the treatment cycles as determined by the investigator.
- 2. To obtain pharmacokinetic data of tTF-NGR.

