7.1 Administration of tTF-NGR

Patients will receive their assigned dose of tTF-NGR as an i.v. infusion via central venous access (PORT-systems allowed) with an infusion duration of 1 hour at a constant rate. The IMP is stored at -80°C and will be thawed, solved in saline and filtered (Millipore filter unit, 0.2 μ m) short before application (see Appendix: Phase I: Rekonstitution tTF-NGR).

Potential side effects and toxicities anticipated can be classified as those related to infusional reactions, venous thrombosis, arterial vascular occlusion and embolism, disseminated intravascular coagulation (DIC), tumor bleeding, antibody formation, liver toxicity, and transient thrombocytopenia (see IMPD). Thus, treatment has to be performed obligatory in-house for the complete application time of 5 days with all appropriate drugs for hypertensive reactions, for fibrinolysis and anticoagulation ready to use and with appropriate transfusions of platelets and red blood cells available and prepared for. Constant back-up and information of the Intensive Care Unit (ICU) of the UKM is mandatory.

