Patients will be evaluated as outlined in the study calendar below. The time-points given are in relation to IMP application. Additional visits will occur as clinically indicated.

Study Calendar for each 5-day cycle

Days (d), hours (h), weeks (w) post IMP	pre (within 1 w)	at inf. stop	1 h	5 h	daily	5 d	weekly	repeat cycles (see left)	monthly from end of IMP application	study period end
History + examination	Х	Х	х	Х	Х	Х	х		х	х
Lab tests (FBC, biochemistry, coagulation)	х	Х	х	х	Х	х	Х		х	Х
Oxygen sats (- = continuous), ECG-monitoring	х	х-	х-	х-	Х	Х	х		х	Х
Investigator to check eligibility	х						х			
Informed consent	Х									
Clinical/blood assessment of AE and toxicity	х	Х	х	х	х	х	х		х	Х
Tumor measurements	х								X (without relation to IMP)	Х
MRI, vascular volume fraction*	Х			Х		Х				(x)
Pharmacokinetics	х	Х	X (see below)	Х	Х	х	х		х	
НАНА						Х				Х
CNS-MRI	х									

^{*,} times are selected by the decision of the investigator, patients in the verification groups are to be evaluated at least in one cycle of therapy

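### Intensive PK sampling ends at 5 hours and the next draw has no clock time, so the late elimination phase is not reliably sampled; the weekly and monthly PK draws can show no residual drug.

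*Combined protocol and SAP*

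**What the plan says.** Section 3.3 lists two secondary objectives, of which the second is "To obtain pharmacokinetic data of tTF-NGR". Section 12.3 says "Blood samples will be collected at the time points indicated in the calendars". It gives the half-life, from earlier patients, only as "is in the range of few hours", and for that reason the calendar's 1-hour point "will be indeed multiple samplings in 30 min intervals for the first 5 hours".

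The PK row of the calendar in section 12, headed "Study Calendar for each 5-day cycle", and of its copy in the synopsis is marked at pre-treatment, infusion stop, 1 h, 5 h, daily, 5 d, weekly and "monthly from end of IMP application". There is no column between 5 h and daily. On the time origin, section 12 says only "The time-points given are in relation to IMP application", which does not settle whether the 5 h run from the start or the end of the infusion.

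The protocol gives no clock time for the daily sample, no quantification limit, no PK parameters, no PK analysis method, and no purpose for the weekly and monthly PK draws. Section 7.1 says that "treatment has to be performed obligatory in-house for the complete application time of 5 days".

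**The concern.** The schedule does not fit the premise it is built on. If the half-life is a few hours, a 5-hour window sees roughly one or two halvings of the concentration. The hours in which the rest of the drug leaves the plasma have no scheduled draw, while samples are spent at weeks and months, when nothing can be left.

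At stake are the half-life, clearance and total AUC that a reader would expect from the PK objective. If they rest mainly on the first 5 hours, a large share of the AUC is extrapolated, and a distribution phase would pull the estimated half-life down. The minimum sample is 7 patients (section 16.1), so there are few profiles over which imprecision could average out.

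**Working it through.** **Inputs from the protocol.** 1-hour constant-rate infusion (section 7.1), once daily for 5 days (synopsis), draws every 30 minutes to 5 h (section 12.3). A draw just before the next infusion falls about 24 - 1 = 23 h after the previous infusion stop.

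**Assumptions, not in the protocol.** Half-life 2-6 h as a reading of the stated range; one compartment; 5 h counted from infusion stop unless noted; 15% error on the log scale. The plan gives no figure that could be reproduced.

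**Coverage and AUC tail.** With k = ln 2 / t½, the share of AUC after time t post-infusion is [(1 - e^-k)/k] × e^(-kt). For t½ = 4 h, k = 0.1733, the bracket is 0.918 and e^(-5k) = 0.420, so the share is 0.918 × 0.420 = 39%.

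| t½ (h) | Half-lives in 5 h | AUC beyond 5 h | AUC beyond 5 h, if counted from infusion start | AUC beyond 12 h | Level at 23 h, % of end of infusion |
|---|---|---|---|---|---|
| 2 | 2.5 | 15% | 21% | 1% | 0.03 |
| 3 | 1.7 | 28% | 35% | 6% | 0.5 |
| 4 | 1.25 | 39% | 46% | 12% | 1.9 |
| 6 | 0.8 | 53% | 60% | 24% | 7.0 |

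At 8 h, 6-40% of the end-of-infusion level remains, and at 12 h 2-25%. Samples at those times are much more likely to be quantifiable than one at 23 h.

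**Precision of the elimination rate, one profile.** CV(k) = 0.15 / (√Sxx × k), where Sxx is the sum of squared deviations of the draw times from their mean. At t½ = 4 h:

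- Planned draws 0, 0.5, ..., 5 h (11 draws): Sxx = 27.5; 0.15 / (5.244 × 0.1733) = 16.5%.
- The same plus a usable 23 h draw: Sxx = 412.7; CV = 4.3%.
- Ten draws at 0, 0.5, 1, 1.5, 2, 3, 4, 5, 8 and 12 h: Sxx = 128.6; CV = 7.6%.
- The same plus a usable 23 h draw: Sxx = 467.2; CV = 4.0%.

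**Where the 5-hour window suffices.** With a less favourable 20% error, the approximate 95% interval for t½ from the 0-5 h draws alone is 1.7-2.5 h (true 2), 2.3-4.4 h (true 3), 2.8-7.0 h (true 4) and 3.7-16.7 h (true 6). A quantifiable 23 h draw narrows the last two to 3.6-4.5 h and 5.2-7.2 h.

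**A slower second phase (illustration).** Take half-lives of 0.75 h and 4 h, with 70% and 30% of the level at infusion end, 15% error, and a log-linear fit to three points. The draws at 4, 4.5 and 5 h give a median t½ of 2.6 h (10-90%: 1.3-9.8 h; about 14% not estimable). The draws at 5, 8 and 12 h give 3.8 h (3.2-4.9 h). The draws at 4.5, 5 and 23 h, if the last is quantifiable, give 3.9 h (3.65-4.2 h).

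**Weekly and monthly draws.** 168 h / 6 h = 28 half-lives, which leaves 2^-28, about 4e-9 of the end-of-infusion level. Even at a 10 h half-life the figure is about 9e-6. If the week is counted from the first infusion of a cycle, the draw falls about 168 - 96 = 72 h after the day-5 infusion, or 12 half-lives at 6 h, and 2^-12 is about 0.02%. The monthly draw (about 720 h) leaves less than 1e-36 at a 6 h half-life.

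**The case against.** A reader might infer that the elimination phase is missed altogether. The protocol does not support that. All the half-hourly draws after infusion stop lie on the decline, and at a half-life of 2-3 h they give a usable slope. What is unsampled is the later part, from 5 to about 23 h.

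A reader might also compare 16.5% with 7.6%, or 2.6 h with 3.8 h, as plan against remedy. That comparison leaves out the daily sample, which is planned. If it is drawn at about 23 h and is quantifiable, the present schedule performs almost as well as the spread one (4.3% against 4.0%). It is also most likely to be measurable where the 5-hour window is weakest, at long half-lives. This objection stands as far as it goes, but it depends on two things that the protocol leaves open. A daily sample taken after the next infusion gives no clean tail, and no quantification limit shows that 0.03-7% of the end-of-infusion level can be measured.

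A third inference would be that weak exposure data undermine the phase II dose. Section 10 rules that out: the level with at most 1 DLT in 6 patients is declared the MTD and recommended for phase II. PK plays no part in that rule and is not among the listed endpoints.

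The sponsor chose the window from earlier patient data that are not shown, and the true half-life may lie at the short end. The calendar also applies to every cycle, so a patient may give more than one profile. Repetition improves precision, but it neither fills the gap after 5 h nor reduces the extrapolated share of AUC. Finally, weekly and monthly laboratory bloods are taken anyway, so the late PK draws add no visits; their cost is small, but no purpose is given for them.

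**Conclusion.** The point holds in limited form, as a cheap improvement. The late elimination phase has no scheduled draw between 5 h and an untimed daily sample. For a half-life of 2-6 h the dense window covers 0.8-2.5 half-lives and leaves 15-53% of AUC beyond it, or 21-60% if the 5 h start with the infusion. At 2-3 h the slope is usable. At about 4 h or more, or with a slower second phase, half-life and AUC depend on a pre-infusion, quantifiable daily draw: at 4 h and 15% error the CV of the elimination rate is 16.5% without one and about 4% with one.

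These sizes rest on the assumed half-life range, error and one-compartment decline, none of which the protocol gives. The conclusion that weekly and monthly draws show no residual drug is far less sensitive to them and still holds at a 10 h half-life. The consequence is confined to the secondary, descriptive PK objective; the MTD and the recommended phase II dose do not change.

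**What to change.** In section 12.3 and in both calendars (synopsis and section 12):

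- Keep about the same number of day-1 draws but spread them, for example pre-dose, infusion stop, then 0.5, 1, 1.5, 2, 3, 4, 5, 8 and 12 h after infusion stop. That is 10 draws from infusion stop onward, against 11 now.
- State that post-infusion times count from infusion stop.
- Fix the daily sample as the pre-infusion sample of days 2-5.
- Drop the weekly and monthly PK draws, or state what they are for. Antibody testing has its own calendar row.

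Without a usable 23 h draw, this lowers the CV of the elimination rate at a 4 h half-life from 16.5% to 7.6%, and the AUC beyond the last day-1 draw from 15-53% to 1-24%. The result then no longer hangs on one late sample. The cost is a wording change and one or two evening draws on day 1, in patients who are in hospital anyway.

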12.4 Adverse events and unexpected toxicities

All adverse events will be assessed by the Investigator for their seriousness, expectedness and relationship to the study protocol. If appropriate, the IMPD will be referenced. Anticipated toxicities are listed in the IMPD. If the tTF-NGR is suspected of causing unexpected serious adverse reactions, SUSAR reporting will be instigated as in section 13 below and the Investigator and sponsor informed immediately. It is the Sponsor's responsibility to report any SUSARs to the Bundesoberbehörde Paul-Ehrlich-Institute complying with the mandated timelines (7 days for fatal and life-threatening events and within 15 days for all others). Additional information will be provided as relevant within the 8 day designated time-frame. The Sponsor will also be responsible for reporting to the Regulatory Authorities, Ethics Committees and Principal Investigators as per current legislation.

12.4.1 Data and safety monitoring board (DSMB) and Trial Steering Committee (TSC)

The Data and Safety Monitoring Board (DSMB) comprises 3 clinicians with appropriate expertise, all of whom are independent of the sponsor and have no involvement in the development of the protocol. The DSMB will consist of Univ.-[name]. [name] (Director, Department of Hematology, University Hospital Essen), Prof. em. [name] (Geschäftsführer, Deutsche Ges. für Radioonkologie), and [name]. [name] (Director Department of Medicine – Hematology and Oncology, University Hospital Hamburg). Procedures governing the convening and execution of tTF-NGR Phase I Study, Study Protocol, Version 10, 28.07.2016

the responsibilities of the DMC will be specified separately in a written DMC Charter. The DSMB will review data on recruitment, safety and data collection and will advise the Trial Steering Committee (TSC) on whether it is appropriate for the trial to continue. The TSC will consist of [name]. [name] (Director Department of Medicine A, UKM), [name]. [name] (Co-Investigator), and [name]. [name] (Trial statistician).

13. Reporting requirements

All patients will be registered on the study enrollment log and data on study endpoints will be kept on Case Report Forms (CRFs) for each subject.

13.1 Definitions of Adverse Events

Adverse Events are defined according to the Directive 2001/20/EC, the European Detailed Guidance CT 3, corresponding to the relevant definitions in the German GCP Ordinance.

Adverse Event (AE)

This is defined as any untoward medical occurrence in the patient administered an investigational medicinal product that does not necessarily have a causal relationship with this treatment. An AE is therefore described as any unfavorable and unintended sign (including abnormal laboratory results), symptom or disease temporally (timely) associated with the use of an investigational medicinal product, whether or not related to the product.

Clarification:

- A pathological finding, improved or unchanged in comparison to its status before first administration of the investigational medicinal product, does not constitute an adverse event.
- Symptoms of the disease under study should not be classified as AEs as long as they are within the normal day-to-day fluctuation or expected progression of the disease, and as long as they are not serious.

• Laboratory test value abnormalities will be reported in the CRF. Abnormal values should not be reported on the AE page of the CRF unless they are associated with a clinically relevant condition.

Adverse Reaction (AR)

An adverse reaction is defined as any untoward and unintended response in a subject to an investigational medicinal product, related to any dose administered. A causal relationship between the investigational medicinal product and the adverse event is at least a reasonably possibility, which means that there are facts or arguments to suggest a causal relationship.

The definition covers also medication errors and uses outside what is foreseen in the protocol, including misuse and abuse of the product.

Serious Adverse Event (SAE)

A serious adverse event is defined as any untoward medical occurrence in the patient administered a pharmaceutical product, which does not necessarily have a causal relationship with this treatment, and that at any dose:

- > results in death
- > is life threatening (at immediate risk of death at the time of the event)
- results in persistent or significant disability/incapacity
- > requires in-patient hospitalization or prolongs existing hospitalization*
- results in a congenital abnormality or birth defect
- is medically significant (i.e. any event which the investigator considers significant but which is not covered by the above.)
- *: Hospitalization means overnight admission. Hospitalization without underlying adverse event (AE) is not an SAE. Examples are:
 - Hospitalization for protocol procedures e.g. chemotherapy, biopsy or monitoring of the study
- Elective hospitalization for a pre-existing condition (i.e. a condition other than tTF-NGR Phase I Study, Study Protocol, Version 10, 28.07.2016 27

the indication for the chemotherapy) that has not worsened

Admission to a rehabilitation centre or hospice.

Unexpected Adverse Reaction

"Unexpected" means that the nature, severity or outcome of the adverse reaction is not consistent with the applicable product information for the investigational medicinal product, which is the current version of the IMPD.

- The term "severe" is often used to describe the intensity (severity) of a specific event. This is not the same as "serious," which is based on patient/event outcome or action criteria.
- Reports which add significant information on the specificity, increase of occurrence, or severity of a known, already documented serious adverse reaction constitute unexpected events.

Suspected Unexpected Serious Adverse Reaction (SUSAR)

A suspected unexpected serious adverse reaction (SUSAR) is a serious adverse reaction that has been judged to be unexpected.

Severity

Severity for each adverse event, including any lab abnormality, will be determined by using the National Cancer Institute Common Toxicity Criteria (NCI CTCAE, version 4.0) as a guideline, wherever possible. The criteria are available online at http://ctep.cancer.gov/reporting/ctc.html. In those cases where the NCI CTC criteria do not apply, severity should be defined according to the general CTCAE definitions of grades (see chapter 9).

Causality

Relationship to study drug administration will be determined as follows:

Reasonable possibility

There are facts or arguments to suggest a causal relationship.

No reasonable possibility

Time relationship is improbable and another explanation is more likely (e.g. disease or other drugs provide plausible explanation).

13.2 Procedures for Adverse Event reporting

All Adverse Events

Toxicity will be monitored from the first study-related procedure (tTF-NGR application) until 8 days post last administration of tTF-NGR. All adverse events including serious adverse events that occur during this period will be recorded in the CRF.

Investigators must record in the CRF (Case Record Form) and the patient notes their opinion concerning details of nature, onset, duration/end, severity, seriousness, relationship to the IMP tTF-NGR and action taken concerning the IMP. Medical terminology should always be used to describe any event. Investigators should avoid vague terms such as "sick". If possible, a diagnosis rather than a list of signs, symptoms and laboratory abnormalities should be given.

All SAEs will also be reported to the Sponsor using the Serious Adverse Event Form.

Serious adverse events (SAE) reporting

The investigator has to report any SAE occurring from the first study-related procedure (tTF-NGR application) until 8 days post last administration of tTF-NGR, including any compassionate use treatment after end of a patient's study period. If the investigator suspects a reasonable causal relationship to the investigational medicinal product in an SAE occurring even later, this event should also be reported to the Safety Desk. SAE reporting has to be done within 24 hours of knowledge by faxing the SAE form to the sponsor's Safety Desk. Personal data have to be replaced by the trial patient number before forwarding any information.

Safety Desk Contact

Zentrum für Klinische Studien (ZKS) Münster

[name]

[name]

Germany

[contact] [contact]

E-Mail: [contact]

Where possible, a diagnosis rather than a list of symptoms should be given. The investigator is responsible for assessing seriousness, severity (CTCAE v4.0) and causality of the SAE. The SAE form should be completed with as much information as possible. The investigator should not wait for full details before making the initial report.

Minimal information to be included in any initial report:

1. Trial patient number

2. Detailed description of the event

3. Details about administration of the IMP

4. Causality assessment of SAE to the IMP

5. Reporting person

The immediate reports should be followed promptly by detailed, written reports. In case of death, an autopsy report should be provided, if any. For reported deaths, the investigator should also supply the competent authority and the Ethics Committee with any information, if additionally requested by them.

All Serious Adverse Events will be followed up until resolution or definite outcome. The investigator will be asked to provide interim and follow-up reports, as necessary, if the SAE has not resolved at the time of initial report. The investigator should answer all queries from the Safety Desk as soon as possible.

Monitoring pregnancies for potential Serious Adverse Events

Pregnancy is not serious by itself. However, if a subject has a positive pregnancy test during trial participation, this is reportable on an SAE form in order to identify and follow-up on outcome of pregnancy and on any congenital abnormalities. The report tTF-NGR Phase I Study, Study Protocol, Version 10, 28.07.2016

should be made as soon as the investigator gains knowledge of the event. Follow-up of a pregnancy will be done using specific additional questionnaires supplied by the Safety Desk if required. Information will be collected as far as covered by consent (information about the partner or about a child needs to be covered by consent of the patient's partner, too).

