Starting dose will be 1 mg/m²/day. Intraindividual dose-escalation will be performed in 1 patient in 0.5 mg/m²/day steps (to a maximum of 8 cycles) upon a rest period of 16 days for the next treatment cycle of 5 days. The maximum number of 8 dose escalations is reached only if stable disease (SD) is ongoing upon 8 cycles of therapy. Dose-escalation is stopped before the maximum number of 8 escalation steps if tumor response, tumor progression or a Dose-Limiting Toxicity (DLT) is observed. If tumor response is observed or if a patient is diagnosed with progressive disease (PD) after ≥ 2 cycles or clinically as judged by the investigator even before 2 cycles, this patient will go off study and will be replaced by a further patient in whom individual dose escalation will be resumed, starting with the highest dose level reached without DLT in the previous patient. When any DLT is observed in this patient, intraindividual dose escalation is stopped and the patient is taken off study. In case of stable disease or response and resolution of the DLT this patient can be further treated on the highest tolerable dose level without DLT until any of the criteria under 7.4 is reached. This treatment will then be given on an individual compassionate-use basis (off study) according to § 34 of the Helsinki declaration (2013, Fortaleza; Post-Trial Provision).

If this first observed DLT is nonfatal, up to 5 more patients will then be treated on the same dose level having caused DLT (verification group). Patients of the verification group will be treated in sequence of each other, thus a patient has to tolerate the first cycle (5 days) and the rest period of 16 days without DLT before the next patient can be added to this verification group.

Upon observation of no additional DLT in the verification group in a minimum of 2 cycles for each patient, dose escalation can be resumed in one patient out of these until DLT (continue as above). The remaining patients in the verification group will be further treated at this dose-level until any of the criteria under 7.4 is reached.

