Upon observation of one more episode of any DLT within the first 2 cycles given to the patients in the verification group, patient accrual to this verification group is stopped with this second patient with DLT and de-escalation by a $0.5 \text{ mg/m}^2/\text{day}$ step is performed in further up to 5 patients. If on the next lower dose level there are $\geq 2 \text{ DLT}$ in 5 further patients (i.e., $\geq 2 \text{ DLT}$ in 6 patients in total on this dose level), de-escalation will continue. In case, patients of the verification group experience DLT in a later cycle (3rd and following), this will be counted as DLT with all consequences, although the procedure of the study was not influenced before such an event occurred.

Dose de-escalation will continue until ≤1 DLT occurs in 5 further patients treated on a specific dose-level, i.e. there are ≤1/6 patients with DLT in total on this dose level. This dose level is declared the MTD and will be recommended for further studies, such as phase II trials (RDPII).

If an observed DLT is fatal, the above dose escalation scheme is modified. Denote this dose d_{fatal} . In the unlikely event that further patients are treated with this dose, treatment in these patients will be stopped at this dose level and the investigator decides how to go on with the treatment in these patients. The next patients will not be treated with the dose d_{fatal} , but on the next lower dose level d_{fatal} - 0.5 mg/m²/day. If on the dose level d_{fatal} - 0.5 mg/m²/day no DLT or not more than 1 DLT is observed that is non-fatal, further patients are treated on the dose level d_{fatal} until any further DLT is observed or 6 patients are included on this dose level in total. Possible later dose escalation to a level at which one death occurred has to be discussed with the data safety board.

Only in the very unlikely event, that DLT occurs at the starting dose or the dose 0.5 mg/m²/day higher, further dose de-escalation below the starting dose level can be performed as described to establish MTD.

The above procedure is constructed so that MTD is defined similarly to a standard 3+3 design. I.e., any dose with observed DLT in $\leq 1/6$ patients is defined to be the MTD, if on the next higher dose level the observed number of patients with DLT is $\geq 2/6$. The following summary visualizes this procedure:

```

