Start 1 pt at 1 mg/m²/day with individual dose escalation at 0.5 mg/m²/day for 5 days every 3 weeks until any DLT (= dose "d1") or to a max of 8 cycles

Verification group (VG) of ≤5 further pts at d1 without indiv. dose esc.

(Verification group (VG) of ≤5 further pts at d1-0.5mg/m²/day without indiv. dose esc. in case a death occurs as DLT)

No further DLT in VG > resume dose escalation: start 1 pt of VG at d1 + 0.5 mg/m²/day (d), then as above

1 further DLT in VG > dose de-escalation d1 - 0.5 mg/m²/d, 5 further pts (d-1(-2))

>1 further DLT: d-1 = MTD

>1 further DLT > dose de-escalation, continue as above
```

Again, if a patient has been taken off the study due to a DLT or progressive disease, the patient may further be treated as follows. If the patient has stable disease or response and the DLT has been resolved, outside the study the patient may be treated

with the study medication on the highest tolerable dose level without DLT (§ 34 Declaration of Helsinki, Fortaleza 2013). In case of progressive disease or if the DLT has not been resolved, different treatment options are offered.

11. Study objectives and end-points

Primary Objectives

To evaluate the maximum tolerated dose (MTD) and the dose-limiting toxicity (DLT) of intravenously (i.v.) infused daily applications of tTF-NGR in patients with cancer (solid tumors and lymphomas), who had obtained all standard treatment known for their disease entity prior to entry on study.

Secondary Objectives

- 1. To determine the perfusion and vascular volume fraction of measurable tumor lesions versus normal reference tissue before and after tTF-NGR application by MRI as a imaging surrogate parameter for biological activity of the IMP.
- 2. To obtain pharmacokinetic data of tTF-NGR.

Primary Safety end-point

Maximum Tolerated Dose (MTD). MTD is the dose below the dose leading to reproducible episodes of Dose Limiting Toxicity (DLT) in at least 2/6 patients. DLT will be characterized by clinical, blood and serum monitoring at specified time points before and during study period.

Secondary Safety end-points

- 1. Occurrence and frequency of inhibition of tumor blood flow as measured by contrast-enhanced Magnetic Resonance Imaging (MRI).
- 2. Occurrence and frequency of tumor response defined as Complete Response (CR), Partial Response (PR), or Stabile Disease (SD) as defined by RECIST criteria.

Descriptive statistics will be used.

12. Patient evaluation and follow-up

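### Section 13.2 stops toxicity monitoring and AE recording 8 days after the last dose, before the DLT-free rest period ends and before every monthly toxicity assessment

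*Combined protocol and SAP*

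**What the plan says.** Section 13.2 sets the safety window: "Toxicity will be monitored from the first study-related procedure (tTF-NGR application) until 8 days post last administration of tTF-NGR". AEs, serious or not, are recorded in the CRF if they occur in that period. A later event must be reported only if it is an SAE that the investigator suspects is related to the IMP.

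Other sections look further ahead:

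- **Section 10, adding verification patients:** "a patient has to tolerate the first cycle (5 days) and the rest period of 16 days without DLT before the next patient" joins.
- **Section 10, resuming escalation:** "Upon observation of no additional DLT in the verification group in a minimum of 2 cycles for each patient, dose escalation can be resumed".
- **Section 10, late events:** if verification patients "experience DLT in a later cycle (3rd and following), this will be counted as DLT with all consequences".
- **Section 12, study calendar:** the row "Clinical/blood assessment of AE and toxicity" is marked weekly, in the column "monthly from end of IMP application", and at the end of the study period.
- **Section 12.2:** toxicity is assessed at the calendar intervals throughout the study period. Section 7.4 runs that period to day 5 of the last dose level plus 3 months.
- **Section 14.8:** liver toxicity is to be followed throughout the study.

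Section 9 defines a DLT by CTCAE grade and causal attribution. It sets no time limit and does not require seriousness.

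**The concern.** The primary endpoint is a count of patients with DLT at each dose level, and the counts are small. A level qualifies at ≤1/6 and fails at ≥2/6. At the level of the first DLT (d1), the summary scheme in Section 10 turns on one event: "No further DLT in VG > resume dose escalation" at d1 + 0.5 mg/m²/day, against "1 further DLT in VG > dose de-escalation" to d1 − 0.5 mg/m²/day. The recording rule should cover at least the time in which the design expects DLTs to be seen, and in a patient's last cycle it does not.

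A site reading Section 13.2 has no instruction to enter a non-serious Grade 3 event found late in the last rest period or at a monthly visit. If such an event is first judged unrelated, no required AE entry exists for a later review of causality or for the safety review by the DSMB.

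**Working it through.** **Inputs.** Infusions on days 1–5 and a 16-day rest (Section 10); monitoring and recording to 8 days after the last administration (13.2); monthly column counted from the end of IMP (Section 12); Study Period to day 5 of the last dose level plus 3 months (7.4). Assumptions: no dosing delay; one month is 28–31 days; three months are 89–92 days.

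**The plan's own cycle.** 5 + 16 = 21 days, which agrees with treatment every 3 weeks.

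**Final cycle.**
- The 13.2 window closes on day 5 + 8 = 13.
- The rest period covers days 6–21.
- Outside the window: days 14–21, i.e. 21 − 13 = 8 days. That is 8/16 = 50% of the rest and 8/21 = 38% of the cycle.
- With the synopsis's 2-week rest, the cycle ends on day 5 + 14 = 19. Then 19 − 13 = 6 days are outside, 6/14 = 43% of the rest. The direction is unchanged.

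**Monthly assessments.** The first falls 28–31 days after the last dose: 28 − 8 = 20 and 31 − 8 = 23 days past the limit. Later ones are further out, so none is inside.

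**Study Period.**
- With one cycle at the last dose level, 13.2 covers 8/92 = 8.7% to 8/89 = 9.0% of the follow-up.
- With two cycles on schedule at that level, the last dose is 21 days later and 68–71 days remain. The share is then 8/71 = 11.3% to 8/68 = 11.8%.

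**Scheduled toxicity assessments in days 14–21.** None if only the monthly column applies after the last dose. If the weekly column continues, one, or two if they fall on days 14 and 21. The calendar does not say which applies.

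**Who is affected.** The 13.2 window runs from the last administration, so a patient who goes on to another cycle is covered during the preceding rest. The gap follows the final cycle only. A DLT on days 14–21 ends study treatment under Section 7.4, which makes day 5 the last administration. The event then lies 14 − 5 = 9 to 21 − 5 = 16 days after it, outside the window. For the decision on the first two cycles, the gap concerns patients who stop after cycle 1 or 2. The documents give no rate for this. The entry minimum of 6 weeks' life expectancy (Section 6.1) is 42 = 2 × 21 days, so early stopping is plausible.

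**The case against.** The strongest reply is that assessment does not in fact stop. Section 13.2 is about reporting, while Section 12.2, the calendar and the Section 10 gate each require toxicity to be looked for. This stands in part: visits remain scheduled and the fault is a contradiction between sections. But 13.2 says in terms that monitoring ends, and it alone sets the AE recording period.

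Second, other provisions catch much of what could be missed. A DLT must be related, so a serious one stays reportable at any time, and the SAE definition includes events the investigator considers medically significant. Laboratory abnormalities and endpoint data go on the CRF (Sections 13.1 and 13), as does the reason for premature termination (Section 17). This stands and narrows the gap considerably. It does not close it: a DLT rests on grade and attribution, and Section 13.1 itself separates severe from serious.

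Third, the route to the MTD is narrow. Resuming escalation needs two cycles in each verification patient, so a patient who stops after cycle 1 cannot satisfy that condition. No day-21 gate is stated after cycle 2. While a patient is still expected to continue, the site would in practice keep watching. In third and later cycles the window moves with the doses. All of this is fair and limits the reach. It leaves the rest after any final cycle, and the ≤1/6 count at a de-escalated level, for which Section 10 states no two-cycle minimum.

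Fourth, Section 12.3 reports a half-life of a few hours, which makes 8 days less arbitrary. It does not exclude later toxicity, and Section 10 itself asks for 16 days.

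**Conclusion.** The concern holds and should be fixed. The mismatch is certain from the text: day 13 against day 21 in a final cycle, and no monthly toxicity assessment inside the 13.2 window. The percentages are shares of calendar time, not of DLTs, and assume no dosing delay.

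The consequence for the MTD is possible but not quantified. One unrecorded DLT can change the path at a level, but need not: if a second DLT goes unrecorded, accrual continues and a later patient may supply another. Its probability depends on DLT onset times and on how many patients stop early, and the documents give neither. The events at risk are mainly non-serious ones of DLT grade after a patient's last dose.

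**What to change.** Reconcile Section 13.2 with Sections 7.4, 10, 12, 12.2 and 14.8. AEs and toxicity should be recorded at least to the end of the rest period after each patient's last cycle (day 21). Preferably they should be recorded at every toxicity assessment already scheduled up to the end of the Study Period. State in the calendar whether the weekly assessments continue through the last rest period or the monthly column takes over.

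The cost is a wording change and some additional CRF entries. If weekly assessments were not meant to continue after the last dose, it may add one assessment. The drawback is that more disease-related events will have to be recorded and attributed in a population with advanced cancer.
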